2.1. Rationale

The Center for Malariaology, Parasitology, and Entomology (CMPE) in Lao PDR over the past two years has completed the National Strategic Plan 2016-2020¹², and new National Surveillance Guidelines that includes case-based surveillance and focal response including RACD. After some setbacks from 2011-2015, there has been major progress and incidence has recently fallen dramatically in several southern provinces, making foci-based active surveillance strategies now feasible in these areas.

Under the current national and regional artemisinin initiative 2 elimination (RAI2E) funding, VMWs and Malaria Posts will be expanded to improve coverage across these provinces. Household-level RACD has yet to be operationalized in southern Lao PDR, but is planned for roll-out over the next year by teams from national, provincial, and district levels. In order to maximize sustainability and impact, this strategy will need to be community-based and target the highest risk populations.

The current management of *P. vivax* cases and G6PD deficiency varies by country; in Laos, current policy states that all *P. vivax* cases are to be tested for G6PD deficiency and only those without deficiency receive a 14-day course of primaquine. Rigorous follow-up of cases to monitor safety and adherence is not conducted, and the use of G6PD testing and primaquine treatment has not yet been widely operationalized.

The research proposed here will evaluate the effectiveness and feasibility of a community-based reactive case detection strategy when combined with the use of HS-RDTs, targeting high-risk villages and forest populations, and *P. vivax* testing treatment adherence after referral to district or provincial-level facilities. Results of this research will have direct implications for continued roll out and sustainability of community-based foci management, and provide practical guidance that other malaria programs can utilize.

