3.3.2. Adherence and safety monitoring

To ensure participants' adherence to their medication and monitor safety, participants will be informed on how to take their medications, about the side effects of the treatment and the importance of compliance to the treatment. In addition to DOT on day 0, The VMW will conduct a day

3, day 7, and day 14 adherence and safety monitoring visit for all individuals treated with primaquine for *P. vivax*, and the VMW will ask a series of questions to determine adherence with each dose, number of remaining tablets, potential adverse events, and reasons for non-adherence or treatment refusal. Participants with phone number will be sent a daily text message to remind them to adhere to their treatment and remind them about any symptoms suggesting serious adverse events. All participants and their family members will be provided a chart to record and track their adherence as well as symptoms that may indicate an adverse event.

The safety risks associated with participation in this trial are expected to be minimal. The study drugs, AL and PQ, are well tolerated first-line treatments and safe for G6PD non-deficient individuals. Prior to drug administration, participants will be asked about known contraindications, and if such contraindications are reported, participants will be restricted from taking the medication.

Drug	Contraindications
AL	Pregnancy, infants < 5kg, prior allergic reaction, any severe disease
PQ	Pregnancy, age < 12months, infants < 10kg, women in first 12 months of breastfeeding, prior allergic reaction, any severe disease, G6PD deficient

The common adverse events reported for each drug are as below:

- AL: headache, dizziness, loss of appetite, generalized weakness, fever, chills, arthralgia, myalgia, nausea, vomiting, and abdominal pain
- PQ: nausea, headache, fatigue, dizziness, hives, chest pain, painless darkening of urine, jaundice of skin and vomiting.

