The Primaquine Roll Out Pharmacovigilance Tool Data Collection Forms (PROMPT) will be used to track the status of individuals treated with PQ. Identification of serious adverse events (SAEs) will occur both passively and actively. As part of the consent process, participants will be instructed to call or visit VMW to report any adverse events that occur between VMW visits. During adherence and follow up visits, the VMW will also ask participants for specific adverse events related to hemolysis. SAEs as well as serious unexpected serious adverse reactions (SUSAR) will be reported to the study management and PI who will report to the data safety monitoring board (DSMB). At each study site, a local physician will be recruited (Local Safety Monitor, LSM) to determine causality and grade of the SAE. All SAEs will be reported to the Pharmacovigilance center of the Ministry of Health (Lao PDR) and the respective IRBs. All potential AEs or SAEs will be referred by VMW to the nearest health center or district hospital for management and documented as per 4.2 below, and the study will reimburse all patient travel and hospitalization resulting from study drug administration.

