A passive case detection system will be employed in both intervention and control villages to help detect and refer any potential SAEs and active follow-ups will be conducted by VMWs on days 3, 7, and 14; VMWs/VHVs will be oriented on potential drug side effects and asked in addition to passively monitor their communities and refer any potentially serious or unexpected AEs. All public health facilities in the nine target districts will be trained on AE reporting procedures prior to implementation of any study activities. A data safety monitoring board (DSMB) will be established to oversee and report on any SAEs that are potentially linked to the administration of AL or SLD-PQ, as outlined in further detail in Section 4.5. The following steps will be taken for all AEs:

The health facility will complete an AE reporting form (Appendix 8.14). The completed form will then be submitted to the Local Safety Monitor (a medical doctor), who with the support of the UCSF project manager will assess if the event is an SAE or unexpected AE based upon specific criteria determined by the DSMB. If determined to be an SAE or unexpected AE, the UCSF project manager will submit the AE reporting form and any accompanying documentation (clinical records, laboratory reports) to the DSMB and the UCSF PI within 48 hours from the identification of the potential SAE.

Upon receipt of the AE reporting form, the DSMB will complete an AE investigation form (Appendix 8.14) within 24 hours to a) confirm if the event is an SAE, and 2) to determine if the SAE was caused by the administration of AL with SLD-PQ as part of this study. If the event is confirmed to meet the criteria of an SAE, the DSMB will submit the completed AE investigation form to the PI, who will submit to the research ethics committees (RECs) at UCSF and NIOPH. The respective RECs will be notified within 24 hours of the DSMB's completion of all potential SAE investigation forms, and within 48 hours of DSMB notification if deemed an AE, but not fulfilling criteria for an SAE.

Travel and hospitalization costs for any SAEs resulting from PQ administration will be covered by the study.

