4.5. Data and safety monitoring plan

The project will follow US National Institutes of Health (NIH) guidelines for establishing a data safety monitoring board (DSMB). The DSMB will be established prior to any data collection as part of this study. The members of the DSMB will serve in an individual capacity and provide their expertise and recommendations. The primary responsibilities of the DSMB will be to periodically review and evaluate the accumulated study data for participant safety, study conduct and progress, and, when appropriate make recommendations to investigators concerning the continuation, modification, or termination of the trial. DSMB will consider study-specific data as well as relevant background knowledge about malaria, adverse events from drugs used in the study, drug resistance, and the participant population under study.

Membership of the DSMB will consist of five independent experts in malaria control, diagnosis, case management and epidemiology, and one member of the research team to advise and clarify study activities for the independent experts. No independent member of the DSMB shall have any conflict of interest with the study team, the organizations funding or conducting the research, or the results of the study. The DSMB will be comprised of experts in the following areas, with an emphasis on local Lao expert participation:

- The study population in Lao PDR (Lao representatives)
- Malaria diagnosis and case management
- Malaria epidemiology
- Biostatistics
- Conduct of clinical trials
- Malaria drug resistance

No data on futility or benefit of the intervention will be estimable during the course of the trial as the timing of outcome data collection precludes developing stopping rules based on outcome data collected during implementation. Safety concerns associated with the wide-scale use of AL + SLD-PQ, although unexpected, will form the basis of development of a stopping rule. The stopping rules

for this trial will be based on detection of a significantly higher rate of mortality, hospitalization for possible drug-related events, or any other SAE in the intervention villages versus rates recorded at health facilities for the control villages. Further, any investigated SAE that results in death that is found to be due to the administration of one of the study drugs will be grounds for stoppage.

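### The stopping rule limits only the control arm's SAE rate to health-facility records, which tilts it toward an apparent excess in the intervention arm

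*Protocol*

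**What the plan says.** Section 4.5 rests the stopping rule on a significant between-arm excess in one of three kinds of event: deaths, admissions that may be drug-related, and, as the last item, "any other SAE in the intervention villages versus rates recorded at health facilities for the control villages". The control rate is tied to facility records. No source is given for the intervention rate, and no denominator, significance level or number of looks is stated. A separate rule covers a death found to be caused by a study drug.

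On how events are found:

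- Section 4.2: "A passive case detection system will be employed in both intervention and control villages to help detect and refer any potential SAEs". The same sentence adds that "active follow-ups will be conducted by VMWs on days 3, 7, and 14", without naming an arm. Public facilities in all nine districts are trained in AE reporting.
- Section 3.3.2, under the interventions: "Identification of serious adverse events (SAEs) will occur both passively and actively". The scheduled visits are on day 3, day 7 and a "day 14 adherence and safety monitoring visit for all individuals treated with primaquine for *P. vivax". "During adherence and follow up visits, the VMW will also ask participants for specific adverse events related to hemolysis". Potential SAEs are referred to a health center or hospital, and the study pays for travel and admission resulting from the study drugs.
- Section 2.1, on current practice: "Rigorous follow-up of cases to monitor safety and adherence is not conducted".
- Table 5 (Section 3.4.2.2) describes the control arm as standard-of-care case management and lists no safety visits. Section 3.4.2.5.3 places the P. vivax referral letter in the intervention areas and follows it with the patient registry and the card for follow-up visits.

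**The concern.** A test between two rates can be read as a difference in risk only if events are found equally well in both arms. Here one arm appears to have an extra route of detection, and the rule does not confine its count to the route that both arms share. The direction is known: extra detection can only add to the intervention count.

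Two things are at stake. The rule could point to harm where there is none, in a trial of 32 clusters. A real excess would also be harder to interpret, because better surveillance would be a ready alternative explanation.

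**Working it through.** The protocol states no SAE rate, boundary or false-signal probability, so there is no figure to reproduce. The check sets the sections side by side, counts the people affected, and then shows how the result depends on what is counted.

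**1. Sources.** Shared by both arms: passive detection and AE reporting by trained facilities (Section 4.2). Added: VMW visits with symptom questions (Sections 3.3.2 and 4.2). The design is therefore passive detection plus an active supplement against passive detection alone.

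**2. Which arm has the supplement.** Section 4.2 does not say. Sections 2.1, 3.3.2 and 3.4.2.5.3 and Table 5 together imply the intervention arm. This is an inference, though a strong one.

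**3. How many people.** Inputs: 720 index cases (Section 3.4.2.4.3); annual parasite index 2.79 for P. vivax out of 6.77 in total, and population 147,798 (Table 1).

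- P. vivax index cases: 720 × 2.79 / 6.77 ≈ 297
- Population per arm: 147,798 / 2 = 73,899
- Share visited: 297 / 73,899 ≈ 0.4%

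P. vivax cases found during reactive case detection would add to this. Patients not given the 14-day course would reduce it.

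**4. False-signal probability with equal true risk.** Assumptions: equal arms, one look, clustering ignored, one-sided exact test at 0.025. The control count is Poisson with mean m. The intervention count is Poisson with mean m + e, where e is the number of events found only at visits, and R = (m + e)/m. Given the total n, the test rejects when P(Bin(n, 1/2) ≥ x) ≤ 0.025. Its probability of rejecting is computed with n ~ Poisson(m(1 + R)) and x ~ Bin(n, R/(1 + R)).

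| Expected control count m | R for e = 10 | False signal, e = 0 | False signal, e = 10 |
|---|---|---|---|
| 5 | 3.0 | 1.1% | 54.2% |
| 10 | 2.0 | 1.5% | 37.3% |
| 20 | 1.5 | 1.7% | 24.9% |
| 40 | 1.25 | 1.9% | 15.5% |
| 100 | 1.1 | 2.1% | 9.0% |
| 400 | 1.025 | 2.3% | 5.0% |

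With e = 3 the figures are 5.0% for m = 20, 3.4% for m = 100 and 2.9% for m = 400. At one-sided 0.05 with m = 20, the probability goes from 3.7% (e = 0) to 35.9% (e = 10).

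**5. Is e = 10 plausible?** It would be 10 / 297 ≈ 3.4% of the visited index cases. The nearest figure in the protocol is the 2015 national study in Section 2, with one serious hematocrit drop among 889 people followed. Applied here, that gives 297 × 1/889 ≈ 0.3 events. That outcome is narrower than any SAE, so it does not bound e, but it marks ten as a high value. Very small counts also rarely trigger the test: five events against none gives 0.5^5 ≈ 0.031, which is not significant at 0.025, and six against none gives 0.5^6 ≈ 0.016, which is.

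**The case against.** Much of the case on the other side stands.

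- Detection is largely shared. A reader might infer that SAEs are sought actively in one arm and only read from records in the other. Section 4.2 does not support that, because the passive system and the facility training cover both arms.
- Intervention events also pass through facilities. VMWs refer potential SAEs, the facility completes the form for every AE, and the Local Safety Monitor reviews SAEs, admissions and deaths across the study areas. The asymmetry is then mainly one of referral into a common system. Review cannot restore control events that never reached that system, so the asymmetry remains.
- The visits are narrow. Section 3.3.2 specifies them for primaquine given for P. vivax, whereas the safety concern named in Section 4.5 is artemether-lumefantrine with single low-dose primaquine. Deaths and admissions depend little on symptom questions.
- A large arm-wide rate ratio is not supported. Assuming 90% capture against 50% for a whole arm would give 0.90 / 0.50 = 1.8, but nothing in the protocol anchors those rates or applies them to everyone. With 90% for the visited 0.4% and 50% for the rest, the ratio is (0.004 × 0.90 + 0.996 × 0.50) / 0.50 ≈ 1.003.
- A reader might infer that a significant result stops the trial automatically. Section 4.5 describes the basis for a rule still to be developed, and the DSMB only makes recommendations.

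A DSMB charter could set the level, boundary and looks. That does not answer the point, because the comparator is already written into Section 4.5.

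**Conclusion.** The point holds as a bias of known direction and unknown size. Section 4.5 compares a rate from unrestricted sources with a facility-recorded rate, while extra detection appears to exist in the intervention arm only. If true risk is equal, the comparison leans toward an apparent excess there.

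The effect is small if all-cause events across whole catchments are counted. It could be material if only rare drug-related SAEs are counted and several of them surface only at visits. The tabulated probabilities are illustrations under assumed counts, one look and no clustering. They are not estimates for this trial. The conclusion also rests on reading the visits as intervention-arm activity. If control patients were visited in the same way, the tilt from the visits would disappear and only the mismatch in named sources would remain.

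**What to change.** In Section 4.5, and in the DSMB charter if there is one:

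- Define the between-arm comparison on the same data source and the same denominator in both arms, for example facility-recorded deaths and all-cause hospitalizations per catchment population.
- Flag events that reached a facility only through a study follow-up visit, and repeat the comparison without them.
- Send every actively detected SAE to the case-by-case DSMB causality review already set out in Section 4.2.
- State in Section 4.2 which arm receives the active visits.
- Leave the rule on a drug-caused death as it is.

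The cost is a change of wording and one extra field on the event form. Non-hospitalized SAEs leave the formal comparison, though each is still reviewed. Some bias remains, because VMW referral and reimbursed care can bring intervention patients into facilities who would not otherwise have come. Deaths and all-cause admissions should be least affected.

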4.6. Collection of specimens

RDT kits for malaria using finger prick blood samples will be collected during the research and intervention. These samples and their byproducts will be collected for disposal according to local disposal standards for biohazard and sharps waste at the nearest health facility (generally incineration). DBS will also be collected for PCR analysis of malaria parasite infection. These blood spots will be disposed of after the research and not stored for future use. The research period will be defined by the approval dates from the local research ethics committee, the UCSF, and ministry of health, and blood samples will not be stored for any longer than three years past the date the research study end. The informed consent documents will specify the uses and storage plans for dried blood specimens. Patient identifying information will be replaced with an unrelated unique identifier on each filter paper. All appropriate universal and site-specific safety precautions will be used in handling sharps, RDTs, and filter paper blood spots. All survey workers will be trained in the proper storage and handling of blood samples prior to fieldwork.

4.6.1. Racial and ethnic origin

A diverse range of ethnic groups will be included in the study, including several marginalized ethnic minorities. Our study will be conducted outside of the U.S., and no racial/ethnic group will be excluded. We do not expect to find race/ethnicity differences in the intervention effect, but refusal rates may differ.

4.6.2. Inclusion of vulnerable subjects – children and pregnant women

All age groups will be included in this study, except for those < 18 months. All children that participate must have the consent of the parent or guardian. Children older than 6 years and less than 18 must also provide oral assent before participation. All women who are pregnant or believe they may be pregnant will be assessed appropriately before treatment.

4.7. Participant consent/assent

Written informed consent will be obtained from the household members, neighbors, and co-workers eligible for the study. For the field procedures (survey, blood testing, treatment and follow-up visits), people will be asked to consent each time they are eligible to be part of the study. Consent will not be required for collection of de-identified, used RDTs from health facilities inside and outside of the study areas, if this collection is deemed feasible.

Consent will be conducted in the participant's household or in a private area prior to study activities. Consents may be collected from all members of the household and/or co-workers once. Parents will be able to sign one form to consent for themselves and all of their participating children (under 18 years old) at once. Each additional adult member of the house will sign separate consent forms. Each minor (12-<18 years old) will sign a separate assent form.

Informed consent will be conducted in local languages. If the participant is unable to read or write, an X will substitute for a signature.

As part of the informed consent process, study personnel will assess participants' understanding of the study procedures that were explained by using a checklist comprised of key components of the study. Participants who pass will be allowed to sign the written consent form. If the participant does not pass, the consent discussion will be repeated, before asking for a signature. In this case, the consent form will be read again, focusing on areas where understanding was limited, and encouraging

the subject to ask questions. Up to five attempts will be permitted per participant. If, despite five consecutive attempts (each incorrect one followed by the team's correction with explanation), the participant still has not answer a minimum number of questions correctly, then he/she will not be allowed to take part in the study.

5 Potential risks, limitations, data quality assurance, and dissemination plan

5.1. Potential risks from participation

Detailed discussion of potential AEs related to drug regimens is discussed above in section 4.2. Finger pricks for RDTs and DBS are associated with small risks of bleeding, hematoma, and infection. To minimize these risks, the skin will be cleaned with alcohol prior to puncture, and sterile unused lancets will always be used, and pressure will be placed on the puncture site after removal of the lancet using sterile gauze. Although the quantity of blood drawn would not lead to any ill effects on the participants' health, some adults and rarely children feel faint from the blood during the finger prick. The risks will be minimized by having trained health staff perform all procedures, and all untoward effects will be evaluated by health center staff.

For those subjects with *P. vivax* diagnosis that are tested for G6PD deficiency, there is a risk of misclassification and wrongly ascribed to being G6PD non-deficient and then being treated with 14 days of PQ. In this study, the team will ensure a high-quality of training for all those using the G6PD RDTs, in addition subjects will be given information on what to do if they experience adverse events, and on days 3 and 14 all subjects given PQ will be actively followed up. If hemolysis is suspected PQ treatment will be stopped and the subject monitored to at least day 14. Should the hemolysis event require further clinical management, the study team will ensure access to appropriate health services.

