4.2. Protection against risks associated with administration of PQ

The main safety concern for primaquine administration is the risk of acute hemolytic anemia in individuals with glucose-6-phosphate dehydrogenase (G6PD) deficiency¹⁷. In a context where G6PD testing is not available, a dose of 0.25mg/kg of PQ has been found to be safe in individuals with any of the G6PD variants and is recommended by WHO¹³. All individuals RDT+ for *P. vivax* will be referred to and tested at a health facility using a G6PD Carestart RDT and a 14-day course of primaquine will only be given to G6PD non-deficient individuals. After the first six months, a subset of VMWs will conduct G6PD testing under supervision by a study staff member for *P. vivax* cases diagnosed in the community. Primaquine is typically well tolerated but possible side effects include nausea, headache, fatigue, dizziness, hives, chest pain, painless darkening of urine, jaundice of skin, vomiting and syncope (fainting). In line with national guidelines, PQ will not be administered to pregnant women in any trimester or to women unable to undergo pregnancy testing, children less than 6 months of age, infants weighing less than 10 kg, women in the first 6 months of breastfeeding, or individuals with prior allergic reaction to PQ or related drugs.

The key to managing side effects and any potential adverse events (AEs) or serious AEs (SAEs) is thorough training of VMWs/VHVs, health facility staff and supervisors, and intensive sensitization of the community. HC workers and VMWs/VHVs will passively monitor their respective communities for AEs and refer any potential SAEs to designated health facilities. Health workers at these facilities will be informed of the project and potential side effects, and undergo training on completion of AE reporting forms (8.14 and 8.15). Cases that cannot be treated at health centers will be referred to district or provincial hospitals.

All participants receiving study drug will be provided with an informational sheet listing potential side effects and instruction to seek care at the nearest health center should they experience any of the defined symptoms or other adverse events. Community sensitization events and targeted IEC/BCC materials will also help increase community awareness of potential adverse events and encourage early care-seeking if events arise.

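### The protocol sets different thresholds for which adverse events after primaquine a VMW refers, and gives an unreferred event no stated route to the Local Safety Monitor

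*Protocol*

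**What the plan says.** Four places in the protocol say when an adverse event after primaquine is referred:

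- Section 3.3.2 (Adherence and safety monitoring): "All potential AEs or SAEs will be referred by VMW to the nearest health center or district hospital for management and documented as per 4.2".
- Section 4.2 (Protection against risks associated with administration of PQ), on monitoring by community workers: "HC workers and VMWs/VHVs will passively monitor their respective communities for AEs and refer any potential SAEs to designated health facilities".
- Section 4.2 again, on passive monitoring in addition to the active visits: VMWs are to "refer any potentially serious or unexpected AEs".
- Section 2.6 (Summary of ethical issues), on early haemolysis in a person misclassified on G6PD status: primaquine is stopped and the person is referred where necessary.

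Section 5.1 (Potential risks from participation) covers suspected haemolysis. Primaquine is stopped, the subject is monitored to at least day 14, and "Should the hemolysis event require further clinical management, the study team will ensure access to appropriate health services". It does not mention referral or reporting.

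The signs of haemolysis are also classified in two ways. Section 3.3.2 ends its list of common primaquine reactions with "painless darkening of urine, jaundice of skin and vomiting", and section 4.2 lists the same signs as possible side effects. Under Case Management and Follow-up in section 3.3.1, jaundice and dark urine are among the symptoms of severe illness for which a person is referred.

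On reporting, section 4.2 introduces its steps as applying to all AEs. The first step is "The health facility will complete an AE reporting form (Appendix 8.14"). The completed form goes to the Local Safety Monitor, a physician, who decides with the project manager's support whether the event is serious or unexpected. Only events so classified go on to the DSMB.

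**The concern.** Section 4.2 calls acute haemolytic anaemia in G6PD-deficient people the main safety concern with primaquine. The safety of G6PD testing and primaquine at community level is a secondary objective. After the first six months, a subset of VMWs test and treat in the community with a staff member's help. The VMW is therefore often the first to hear of a possible reaction.

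If the VMW's instruction depends on which section was used in training, similar events will be handled differently in different catchments. Section 4.2 gives the judgement of seriousness to a physician working from a form. Under the narrower referral wordings the VMW makes that judgement first, before any form exists. What is at stake is complete and uniform physician review of possible haemolysis.

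**Working it through.** No arithmetic applies. The check sets the sections side by side and follows one event through them.

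**Step 1. Do the rules cover the same events?** Section 3.3.2 covers events found at the day 3, 7 and 14 visits, and events that participants report to the VMW between visits. Both wordings in section 4.2 concern passive monitoring. A reaction that a participant brings to the VMW between visits falls under both sections, so they overlap.

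**Step 2. Follow one event.** Take a participant on the 14-day course who tells the VMW of dark urine. The VMW does not think it serious.

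| Source | What the text leads to |
|---|---|
| 3.3.2 | Referred, as are all potential AEs |
| 4.2, potential SAEs | Referral not required by this wording |
| 4.2, potentially serious or unexpected | Referral not required if the VMW treats a listed reaction as expected |
| 2.6 | Depends on whether referral is thought necessary |
| 3.3.1, severe-illness list | Referred, if the list is read as applying during follow-up |
| 5.1 | Stop and monitor; referral and reporting not mentioned |

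The first four rows set different thresholds. The fifth conflicts with reading the sign as a common reaction. The sixth sets no threshold but describes handling that ends without a report.

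**Step 3. What follows if the VMW does not refer?** The section 4.2 steps begin at the health facility. Facility staff are trained to complete the AE forms (4.2), and VMWs are trained to detect adverse events (3.4.3.5, Outcome 4). No step has the VMW complete or send the form. The text is thus inconsistent within section 4.2: the steps are for all AEs, but the first can happen only for an event that reaches a facility.

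**Step 4. What other routes exist?**

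- Section 4.2 tells participants given study drug to seek care at the nearest health center for the listed symptoms or other events, so a form can follow without referral. Section 3.3.2, however, tells them to call or visit the VMW.
- Section 3.3.2 sends SAEs and SUSARs to study management and the PI, and from there to the DSMB. This begins once an event is recognised as serious.
- Section 4.5 has the Local Safety Monitor review all SAEs, admissions and deaths. This begins with recognition as serious, admission or death.
- PROMPT forms track people treated with primaquine (3.3.2). The text states no route from them to the Local Safety Monitor.

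**Step 5. What is left over?** An event that the VMW hears of, judges non-serious and does not refer, in a participant who does not go to a facility and is not admitted. For that event the protocol states no route to the Local Safety Monitor.

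**The case against.** The strongest reply has four parts.

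**Scope.** Section 3.3.2 is the rule for study participants, while the two wordings in 4.2 concern passive community monitoring, one of them expressly on top of the active visits. Neither says that other events must not be referred. This softens the conflict. It does not remove it, because 3.3.2 also takes in events reported to the VMW between visits and then points to 4.2 for documentation.

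**Signs already covered.** Section 3.3.1 names jaundice and dark urine as grounds for referral, under a heading that includes follow-up. This is a fair point, and a VMW trained on that list would refer. But the list concerns severe illness and can be read as applying at presentation, and 3.3.2 places the same signs among common reactions. The two need reconciling.

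**Section 5.1.** The sentence quoted from it names no VMW, sets no referral threshold and excludes nothing, and the section points to 4.2 for detail. This stands. The direct conflict is between 3.3.2 and sections 4.2 and 2.6; 5.1 adds only silence on reporting.

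**Unseen forms.** The treatment follow-up form (Appendix 8.24) and the PROMPT form (Appendix 8.25) may carry a route to the Local Safety Monitor. They are not shown, so this cannot be excluded. The protocol text should still state the route.

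**Conclusion.** The point holds in a limited form. The referral thresholds in 2.6, 3.3.2 and 4.2 differ, dark urine and jaundice are classified in two ways, and the reporting steps for all AEs omit an event that a VMW handles without referral. The gap concerns events that a VMW judges non-serious, and it lies at the Local Safety Monitor. This rests on reading the protocol text without the appendix forms.

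A reader might infer more, but the documents do not support it:

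- *That only referred events get a form.* Participants can go to a facility themselves.
- *That haemolysis can bypass safety review or the DSMB altogether.* Recognised SAEs and SUSARs reach the DSMB through the PI, and the Local Safety Monitor reviews SAEs, admissions and deaths. Under 4.2, an event classified as non-serious and expected would not go to the DSMB even if it had been referred.
- *That the referral rule determines the safety result.* The AE rate also draws on intervention data and VMW visits (3.4.1), and haemoglobin is measured before and after treatment in people receiving primaquine (3.4.3.2).
- *That the number of missed events can be estimated.* The expected case count in 3.4.2.4.3 is not a count of people treated with primaquine, and the protocol gives no rate for these signs in them.

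The matter should be corrected because it affects physician review for a stated safety objective and is cheap to put right.

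**What to change.** 1. Reconcile sections 2.6, 3.3.1 (severe-illness list), 3.3.2 (referral sentence and list of reactions), 4.2 (both wordings) and 5.1 into one referral rule for adverse events and suspected haemolysis. The sponsor's clinicians should choose the rule; this review takes no position on which is right.
2. As a reporting change only, state in section 4.2 that any adverse event or suspected haemolysis that a VMW finds or is told of is recorded on the existing AE reporting form (Appendix 8.14) and sent to the Local Safety Monitor, whether or not the patient is referred. Cross-refer to this from 3.3.2 and 5.1.

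The cost is protocol and SOP wording, brief VMW training on a form that only facility staff are now to complete, and a few more forms for the Local Safety Monitor to read.
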